Intervention Feature & Description	Scientific rationale	Paradata metrics ^a				

HMP Forums: Discussion boards where users can start new discussion threads or respond to or "like" content posted by other participants.	Pre-populated thread topics will correspond to stigma framework constructs.	# of: posts created, posts read/liked; total time spent; content of posts
Knowledge Center: Brief articles on health and wellness tailored for YBLMT, including featured sections on HIV/STI prevention and care.	Content will correspond with original HMP intervention, and aligns with the Integrated Behavior Model.	# of: articles read, quizzes completed; total time spent
Provider Platform: HIV/STI/sex questions answered by a prevention and HIV care doctor within 72 hours.	Provide evidence-based answers to users' health questions, including linkage to care.	# of: posts created, posts read; total time spent; content of questions
User Profile: Profile page showing participant's username, favorites, and badge progress.	Personalization and gamification features may incentivize continued user engagement.	# of: times visited, badges earned
Test ordering: Ability to order HIV self-test kit.	Provide an opportunity to get tested if users experience barriers to get tested locally.	# tests ordered

^a Each unique user action on HMP will be captured with date and timestamps.

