5.4.3 HIV Testing

Participants who self-report as HIV negative or unknown will be able to request up to 3 in-home OraQuick HIV tests. These HIV tests help maintain equipoise with the HemaSpot procedures for HIV-positive counterparts in the trial. We have made these HIV test kits optional. Some participants may benefit from an in-home test if they experience HIV stigma in their communities, yet others may prefer to get tested in-person (e.g. at a local community-based agency, primary care doctor, or testing bus). We will ask participants to upload a photo to the app of the HIV test stick that shows their test result. This is also an optional activity. In post hoc analyses, we will compare those who requested in-home test kits with those who report testing at community agency in the follow-up assessments. If participants report a HIV positive result (whether through in-home test kit testing results, a flagged HIV status change in their follow-up surveys, or by notifying the study team directly in the app), our Care Navigator will reach out within 3 business days to support and facilitate linkage to resources and care, including identifying a convenient location for confirmatory testing (if needed) at a local agency. The study team will not report HIV positive OraQuick results to local health departments, as this is a screening test, not a diagnosis. The Care Navigator will encourage and support participants in seeking confirmatory testing and linkage to care for the remainder of their time in the study.

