10.0 STATISTICAL/ANALYTIC CONSIDERATIONS

10.1 Introduction

10.1.1 Paradata Metrics

We will measure temporal engagement by examining users' visits to the app and time spent on app using HMP's paradata timestamps at each login and logout. The paradata will also include information allowing us to link engagement for users who create, like, read, or otherwise interact with content in the app. We will also calculate scores for each participant based on their levels of "active" (posting, commenting) and "passive" (reading) engagement. Active engagement scores will be calculated by assigning one point for each time a participant posted or commented on app content. Passive engagement scores will be calculated using the paradata database to assign a participant one point for each time they read content. Aggregate engagement scores for each participant will be included as indicators and latent factors, as appropriate, in our analyses. This strategy will allow us to examine how different forms of engagement (e.g., temporal engagement, active engagement, passive engagement) influence our study outcomes.

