10.3.2.1 Quantitative Analyses

Building our theoretical framework, we will use structural equation modeling (SEM) to test whether engagement with stigma content predicts changes in stigma-related outcomes over time (e.g., decreases in anticipated HIV stigma), and changes in HIV care outcomes over time (e.g., repeat HIV testing; consistent VS). In these HIV-stratified analyses, we will use latent class analysis to characterize users' engagement in the app. We will estimate the independent contributions of passive and active engagement on both stigma and HIV outcomes, as well as how cumulative engagement in stigma-related discussions influences these outcomes. Key sociodemographic predictors will be included as covariates (e.g., age, time since diagnosis). We will also examine the contribution of specific mediators (e.g., social support) in these models by decomposing the total effects into direct and indirect effects. In exploratory analyses, we will use multigroup SEM analyses to test whether these proposed models differ based on latent classes of users (e.g., active forum contributors vs. lurkers; low, moderate, high engagement). Multigroup analyses allow us to compare the strength and direction of the effect sizes in our models and their overall fit across these engagement groups. Ideal models will have values of .90 or higher among fit indices and values of .06 or lower for RMSEA as acceptable indicators.85 The proposed study has sufficient power to carry out these subsample analyses in our model identification and model testing stages. MacCallum et al.²²⁰ show that power of .80 is achievable with alpha=.05 and 30 degrees of freedom in cross-sectional analyses with a sample of 366 for a close model fit (for df=100 the minimum sample size is 178). Thus, we have ample power for these SEM analyses, even when dividing the sample by HIV status or engagement profile.

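### In the HIV-negative Aim 2 analysis, app visits and time include the sessions used to order and document home HIV tests, so engagement can appear to drive testing when it does not

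*Combined protocol and SAP*

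**What the plan says.** Section 10.1.1 defines three forms of engagement.

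- **Temporal:** "We will measure temporal engagement by examining users' visits to the app and time spent on app", taken from login and logout timestamps. No type of session is excluded.
- **Active:** "Active engagement scores will be calculated by assigning one point for each time a participant posted or commented on app content".
- **Passive:** the paradata are used to "assign a participant one point for each time they read content".

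The section then says "Aggregate engagement scores for each participant will be included as indicators and latent factors, as appropriate, in our analyses", and that all three forms will be examined for their influence on study outcomes.

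Section 10.3.2.1 adds that, in analyses stratified by HIV status, "we will use latent class analysis to characterize users' engagement in the app". It names repeat HIV testing among the outcomes. Section 5.4.1 places the mediation question across the 12-month follow-up.

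The app is also one route to the outcome. Table 1 in section 3.3.2 lists the feature "Test ordering: Ability to order HIV self-test kit" and gives the number of "tests ordered" as its paradata metric. Section 5.4.3 says "We will ask participants to upload a photo to the app of the HIV test stick that shows their test result", and section 8.2 pays $20 per upload. Sections 10.2 and 10.3.1 define success for HIV-negative participants as two tests at least 3 months apart within 12 months. Up to three kits are available.

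**The concern.** Each home test ordered through the app adds at least one login to the engagement measure, and a second if the photo is uploaded in a separate session. The same test counts toward the outcome. Part of the outcome is therefore contained in the predictor. Engagement is also aggregated per participant over the window in which the outcome is scored, so app use after the second qualifying test can count as explaining it.

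Section 2.2 makes mediation by engagement a secondary objective. If visits or time were associated with routine testing, the analysis as planned could not tell whether app use led people to test or whether people logged in to get a test. Latent classes built on visits or time could partly sort testers from non-testers.

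**Working it through.** The plan states no figure for the association between engagement and testing, so there is none to reproduce. The check asks how large the association can be when no true link exists.

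**Inputs from the documents.** HIV-negative intervention participants: 150 in Arm 1, plus half of about 300 referred peers in Arm 2 (section 3.2), so 150 + 150 = 300. Up to three kits each. Success is two or more tests. Alpha is 0.05, as in the power statement of section 10.3.2.1.

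**Assumptions, not in the documents.** Other visits are independent of testing and over-dispersed (gamma-Poisson, shape 1), so their SD is √(μ + μ²) for mean μ. Each kit brings two visits. Home tests (0/1/2/3) have probabilities 0.40/0.25/0.20/0.15 (60% of users take at least one) or 0.70/0.15/0.10/0.05 (30%). In-person tests (0/1/2) have probabilities 0.5/0.3/0.2. The 3-month spacing rule is not imposed.

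**Step 1: the built-in gap in visits.**

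- *60% use kits.* P(fail) = 0.40×0.5 + 0.40×0.3 + 0.25×0.5 = 0.445, so P(success) = 0.555. Mean home tests overall = 0.25 + 0.40 + 0.45 = 1.10. Among failures: 0.125/0.445 = 0.281. Among successes: (1.10 − 0.125)/0.555 = 1.757. Gap = 2 × (1.757 − 0.281) = 2.95 visits.
- *30% use kits.* P(fail) = 0.70×0.5 + 0.70×0.3 + 0.15×0.5 = 0.635, so P(success) = 0.365. Mean overall = 0.15 + 0.20 + 0.15 = 0.50. Among failures: 0.075/0.635 = 0.118. Among successes: (0.50 − 0.075)/0.365 = 1.164. Gap = 2 × (1.164 − 0.118) = 2.09 visits.

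**Step 2: what that gap does to a test.** With d = gap/SD, z ≈ d·√(300·p·(1 − p)), where p is P(success). The rejection rate is about Φ(z − 1.96) + Φ(−z − 1.96). For 60% kit use and 10 other visits: d = 2.95/10.5 = 0.28, z = 0.281 × √(300 × 0.555 × 0.445) = 2.42, and the rate is about 68%. The simulated columns come from logistic regression of success on visits alone; their ranges span the two kit-use settings.

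| Mean other visits | SD | d (60% / 30% kit use) | Approximate rate, untransformed | Simulated, untransformed | Simulated, log visits |
|---|---|---|---|---|---|
| 10 | 10.5 | 0.28 / 0.20 | 68% / 38% | 37–74% | 73–98% |
| 20 | 20.5 | 0.14 / 0.10 | 24% / 14% | 14–26% | 34–66% |
| 40 | 40.5 | 0.07 / 0.05 | 10% / 7% | 5–8% | 13–31% |
| 100 | 100.5 | 0.03 / 0.02 | 6% / 5% | about 5% | 4–12% |

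On the log scale, the false odds ratio per SD was 1.4–1.6 at 10 other visits, 1.2–1.3 at 20 and 1.1–1.2 at 40.

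**Step 3: sensitivity.** The figures below are for 10, 20 and 40 other visits.

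- One visit per kit, untransformed: 15–24%, 5–10% and about 7%.
- Only 15% of users taking a home test, log visits, two per kit: 28%, 8% and 5%.
- Kit-related visits removed: 4–6%.

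**Step 4: a second model with different assumptions.** About 44% meet the outcome, each kit brings 2–3 visits, and there are 10–100 other visits.

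- Untransformed visits: 4–5% if no tests use kits, 6–24% if a quarter do, 7–62% if half do. If all do, 26% at 40 other visits and 99.7% at 10.
- Log visits, half of tests by kit: 8–94%.
- Post and read scores: 3–8%, OR per SD about 1.0.
- Number of tests ordered used as the metric: 100% when a quarter to half of tests use kits.
- Visits in months 0–6 against testing in months 6–12, kit visits kept: 4–10% with up to half of tests by kit. With all by kit, 6% at 40 other visits and 39% at 10. A lag alone does not always remove the problem.

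Time in the app was not simulated. Its overlap follows from the definition.

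**The case against.** The other side has several sound points.

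- **The main Aim 2 predictors are different ones.** Section 10.3.2.1 centres on engagement with stigma content and on active and passive engagement. None of these contains an ordering or upload step, and it does not name visits or time. This stands, and it limits the point. But section 10.1.1 commits to examining temporal engagement against outcomes, and the latent classes are not restricted to the other scores.
- **A reader might infer from Table 1 that tests ordered is an Aim 2 mediator.** The documents do not say so. It is the log metric of one feature and not one of the section 10.1.1 scores. The plan permits its use but does not state it.
- **The app is only one route to testing.** Kits and photo uploads are optional and in-person tests count (section 5.4.3). The artefact is therefore possible, not certain.
- **The largest figures rest on choices the plan does not make.** The log transform, two visits per kit and few other visits are assumptions. With untransformed visits and 40 or more other visits, the artefact nearly disappears.
- **No mediation model was run.** The simulations use one predictor and no arm effect. Control participants can order kits too, so the overlap exists in every arm. A reader might infer that the mediation question would be answered yes by circularity, or that any indirect effect would be inflated. Neither is shown.
- **A reader might extend the point to viral suppression**, because HemaSpot instructions can be viewed in the app. Those kits are mailed on schedule with a printed booklet (section 5.4.2). In-app viewing might affect whether a sample is returned, but not whether the virus is suppressed.
- **Aim 2 is exploratory**, and the primary comparison of arms is untouched. Both are true, but section 2.2 still lists the question as a secondary objective.

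**Conclusion.** The point holds for one stratum and one family of measures: visits and time in the app, and latent classes built on them, against routine testing in HIV-negative and status-unknown participants. There the predictor contains part of the outcome, the windows coincide, and no rule on time order is stated. Post, comment, read and stigma-content scores share only the open timing.

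The size cannot be fixed from the documents. Under the assumptions above, false positives at a nominal 5% run from about 5% (many other visits or low kit use) to over 90% (few other visits, high kit use, log visits). These figures show that a spurious association is possible. They do not estimate bias in the planned structural equation model. The documents support saying that engagement can appear to drive testing, not that it will.

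**What to change.** In sections 10.1.1 and 10.3.2.1, for every analysis against HIV testing:

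1. Compute visits, time and latent engagement classes after removing whole sessions devoted to kit ordering, tracking or photo upload. In mixed sessions, remove at least the time spent on those steps. Dropping only the actions is not enough, because visits and time come from login and logout.
2. State that the number of tests ordered is not used as an engagement indicator.
3. Count only engagement that precedes the outcome event. Compare participants at the same study time, so that those who never meet the outcome do not accrue engagement for longer.
4. As a sensitivity analysis, relate filtered engagement in an early window to later testing, adjusting for earlier testing. The choice of window is debatable and the 12-month outcome should not be redefined around it, so this should not replace the main analysis.

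No new data are needed, because the footnote to Table 1 says that every user action is date- and time-stamped. The cost is some paradata filtering and slightly less engagement data in the testing analysis.

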10.1.2 Mixed-Methods Paradata Forum Coding

Expanding on the procedures developed and successfully employed in our R21,49 we will conduct a mixed-methods analysis of user-contributed content to the forums. All content and associated paradata of each user post will be captured by HMP's backend database. We will use Dedoose cloud-based qualitative data analysis program to catalogue and code all instances of stigma-related content and characterize their potential contributions to HIV risk and care behaviors. First, two coders will independently identify all posts that contain stigma-relevant content. Next, they will conduct a content analysis to categorize the nature of the coded stigma content as enacted, community, anticipated, internalized, or challenged stigma. Coding discrepancies will be reviewed and resolved by a third analyst. Ongoing analysis progress will be discussed during biweekly YAB meetings and feedback sought on YAB members' interpretations of participant forum conversations and emergent themes. The final coded dataset will be used for qualitative analyses and publications, as well as to create user-specific variables representing their engagement with each type of stigma-related domain. These data will be used to examine how engagement with stigma content is associated with changes across HIV outcomes (HIV testing, VS) directly and through proposed mediators (e.g., social support and isolation, substance use, depression). We successfully used this methodology in our R21 analysis and have established analytic protocols to carry out these procedures.49-51

10.2 Power Estimates

The primary outcome for the proposed trial is stratified by HIV status and defined as *successful* engagement in care. For HIV-positive participants at baseline, we define successful engagement in HIV care as consistent VS across the 12-month trial (per IOM guidelines²¹⁸). For HIV-negative

or sero-unknown at baseline, we define successful engagement in care as participation in routine HIV testing (2 HIV tests with at least 3 months apart from one another, per CDC guidelines²¹⁹). We define power as correctly identifying the difference in the proportions of YBLMT with serospecific engagement in HIV care within 12 months of each intervention arm (2 arms: HMP Stigma with researcher-created network, HMP Stigma with peer-referred network) to the control arm (Information Control), thus powering for 3 independent hypothesis tests. Our sample size calculations are based on pair-wise HIV-stratified comparisons of the 3 groups in terms of proportion of successful engagement using a two-sided significance level of 0.05 altered by the number of comparisons using a Bonferroni adjustment (significance level is 0.017 for 3 comparisons). To have 80% power to detect a minimum effect size (OR=1.9) of successful engagement in care between the 3-arm trial, we will require at least 450 HIV-negative and 450 HIV-positive participants to detect a 17% difference in successful engagement in. In the event of a 20% loss to follow-up, we will have sufficient power to detect an OR=2.1 (18% difference) at alpha=.017. Participants may continue the study even if they miss an assessment intermittently. We will compare those who completed different follow-up interviews with those who did not on key baseline predictors to check for possible sampling bias. Our analysis will use ITT as appropriate.

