Multiple stigmas related to sexuality, race, and HIV infection negatively impact HIV testing, engagement in HIV care, and consistent viral suppression (VS) among young Black or Latino men who have sex with men and transgender women (YBLMT). At present, few interventions have addressed the effects of intersectional stigma among HIV-infected and uninfected populations. In response to the National Institutes of Health RFA-MH-18-606, this study tests whether a smartphone application (app) intervention tailored for intersectional stigma amelioration can elicit online social support, promote intervention engagement, and mitigate the impact of multiple stigmas on HIV-related outcomes. We will recruit and enroll 1,050 young (ages 15-29), racially and ethnically diverse men who have sex with men and transgender women affected by HIV across the United States. Using a HIV-status stratified randomized trial design, participants will be assigned into one of three conditions (information-only control, a researcher-driven social network intervention, or a peer-referred social network intervention). Behavioral assessments will occur at baseline, 3, 6, 9 and 12 months; biomarkers (viral load) are scheduled for baseline, 6 and 12 months (for HIV-positive participants). HIV negative/status unknown participants may order through the app up to 3 HIV OraQuick self-tests.

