The primary outcome is stratified by HIV status and defined as successful engagement in care (consistent VS for HIV-positive participants and routine testing for HIV-negative participants). The specific aims are: 1) Test whether a smartphone application (app) intervention that promotes usergenerated content and engagement to address intersectional stigma is associated with improvements in the HIV prevention and care continuum (HIV testing, antiretroviral adherence, VS) as compared to an information-only control arm; 2) Explore whether user engagement, as measured by quantitative and qualitative paradata, mediates the intervention's stigma- and HIV care-related outcomes; and, 3) Examine how changes in intersectional stigma and improvements across the HIV care continuum vary between the researcher-driven vs. peer-referred social network intervention conditions. Our research study is innovative given its focus on intersectional stigma as a key target of intervention, and its ability to assess how different kinds of online social network structures influence participants' engagement over time, reduce experiences of intersectional stigma, and improve successful engagement in care. This research addresses a critical need to reduce the effects of multiple stigmas in a priority population using an intervention delivered through a highly appealing, widely utilized technology. If effective, this form of stigma amelioration via online support can be broadly disseminated to reduce HIV transmission and improve care among YBLMT.

STUDY SCHEMA

	Baseline	3 mo	6 mo	9 mo	12 mo
Survey (all pts)	V	✓	✓	✓	✓
HemaSpot (HIV+ pts)	V		✓		✓
HIV Home Test (HIV- pts)	pts may request <=3x and must be >=3 mo apart				

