4.0 SELECTION AND ENROLLMENT OF STUDY PARTICIPANTS

4.1 Inclusion Criteria (All study arms)

- Aged 15-29 years (inclusive) at time of screening
- Identify as Black/African American and/or Latino/Hispanic
- Current U.S. resident (verified by zip code)
- Speak and read English
- Report anal intercourse in the past 6 months
- Assigned male sex at birth (no restrictions on current gender identity)
- Has a smartphone
- If HIV-positive, does not report a hemophilia diagnosis or current use of anti-coagulation medication

Additional Inclusion Criteria (Referred Peers from Peer-Referral Arm)

- Invited by current participant in Intervention Arm 2 (approximately 300 participants)
- Any race/ethnicity

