5.2 Locator/Contact Information

Once a participant has been consented, enrolled, and downloaded the study app, they will be asked to provide a phone number in addition to their email address where they can be reached. Participants will also be asked to provide their mailing address so we can send their HIV test kit or HemaSpot device to them. Study staff will not send mail unless the participant has confirmed their mailing address and is aware they will be receiving a package. The app will assure participants that HIV test kit and HemaSpot packaging does not reveal their participation in a research study. Additionally, the app will tell participants that all email and text message correspondence will not include any protected health information or information related to study participation.

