6.2 Clinical and Laboratory Evaluations (if applicable)

6.2.1 HemaSpot Testing

 HIV-positive participants submit HemaSpot devices by mail for viral load testing at baseline, 6- and 12-month follow-up points.

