10.3 Statistical Analysis Plan

10.3.1 Specific Aim 1:

Specific Aim 1 is to test whether a smartphone application (app) intervention (HMP Stigma) that promotes user-generated content and engagement to address intersectional stigma is associated with successful engagement in care as compared to an information-only control arm consisting of online informational articles and resources curated for YBLMT. Clinical and demographic characteristics will be described for the entire sample, and by treatment group. These will be compared between treatment groups using ANOVA or Kruskal-Wallis test for continuous variables, and chi-square tests for categorical variables. We will conduct primary analyses of our successful engagement in care outcome using logistic regression analyses to compare each active treatment group to the control in pairwise comparison tests at an adjusted significance level of 0.017 to reduce Type-I errors in our 3-arm trial. This approach allows us to also test for differential efficacy between the two intervention conditions (i.e., Does peer-referral HMP outperform the researcher-created HMP arm?).

Logistic regression analyses will be stratified by serostatus. The regression will be run with group assignment only in the model. Among HIV-positive participants, we will examine how intervention conditions influence YBLMT's likelihood of consistent VS over 12 months. We will also test intervention effects on retention in care per IOM guidelines (i.e., proportion of HIV-positive participants who obtain at least 2 viral load tests (at least 3 months apart) within 12 months). For HIV-negative YBLMT, we will compare the proportion of participants who obtain at least 2 HIV tests (at least 3 months apart) within 12 months across arms. Estimates will be calculated and presented with corresponding 95% exact binomial confidence intervals. In secondary outcome analyses, we will compare arms across other HIV care continuum outcomes, as well as stigmarelated (e.g., reduction in HIV-related stigma) outcomes, using a logistic regression with group assignment on the model assuming no imbalances due to successful randomization.

10.3.2 Specific Aim 2:

Specific Aim 2 is to explore whether user engagement, as measured by paradata, mediates the intervention effects observed in stigma and HIV care outcomes.

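### The HIV-positive primary endpoint does not say whether the baseline viral load counts; if it does, the endpoint measures only maintenance of suppression and misses suppression newly gained

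*Combined protocol and SAP*

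**What the plan says.** Section 10.2 sets the HIV-positive primary outcome: "we define successful engagement in HIV care as consistent VS across the 12-month trial". Section 10.3.1 repeats it in similar terms: "we will examine how intervention conditions influence YBLMT's likelihood of consistent VS over 12 months". Neither section lists the contributing time points.

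The specimen schedule is in section 6.2.1: "HIV-positive participants submit HemaSpot devices by mail for viral load testing at baseline, 6- and 12-month follow-up points". No passage says that the baseline result is part of the endpoint, and none says that it is excluded. Section 5.4.4 refers to a Table 2 of outcomes that does not appear in the text available for review.

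Other provisions bear on the point:

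- **Eligibility.** The only entry criterion specific to HIV-positive people is in section 4.1: "If HIV-positive, does not report a hemophilia diagnosis or current use of anti-coagulation medication". Section 4.2 mirrors it. Nothing selects on viral load, so suppressed and unsuppressed people may both enrol.
- **Aim.** The Study Abstract asks whether the app "is associated with improvements in the HIV prevention and care continuum (HIV testing, antiretroviral adherence, VS".
- **Model.** Section 10.3.1 says of the primary logistic regression: "The regression will be run with group assignment only in the model".
- **Timing of the baseline kit.** In section 5.1, randomisation follows the baseline survey, and the mailing address is entered when the app account is created. Section 5.2 agrees: "Once a participant has been consented, enrolled, and downloaded the study app, they will be asked to provide a phone number", with the mailing address requested at the same stage. Section 8.2 allows 45 days from receipt to return a kit and still earn the incentive.

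**The concern.** The baseline specimen is meant to reflect care before the intervention could act. If it is one of the results that must be suppressed, a participant who is unsuppressed at baseline and suppressed at months 6 and 12 is scored a failure in every arm. That participant shows exactly the change that the abstract calls an improvement. Section 1.1 reports that suppression rose in both arms of the earlier trial of this intervention, so such gains are to be expected.

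The primary test would then see one of the two ways in which the intervention can work, and would carry a block of failures fixed at entry. A real effect on gaining suppression could be reported as no effect.

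The silence is also a problem in itself. Two admissible readings of the primary endpoint give materially different power, and the choice between them could be made after data are seen.

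**Working it through.** **The plan's own figure.** Section 10.2 states 80% power for an odds ratio of 1.9, described as a 17-point difference, with 450 HIV-positive participants (150 per arm, section 3.2) at two-sided 0.017. No control rate is given. I used a pooled-variance normal approximation and scanned control rates. Power is highest near a control rate of 42%: the odds are 0.42/0.58 × 1.9 = 1.376, so the intervention rate is 1.376/2.376 = 57.9%, the difference is 15.9 points and power is about 65%. Reaching 80% needs about 205 per arm (615 in total). The stated figure is therefore not reproduced. That is a separate issue, but it means that the power figures below start from a ceiling of about 65%, not 80%.

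**Inputs.** From the documents: 150 per arm, two-sided alpha 0.017, odds ratio 1.9. Assumed, because the documents give no rates:

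- s, the share suppressed at baseline: 0.50-0.80
- m, the control probability of suppression at months 6 and 12 if suppressed at baseline: 0.80-0.90
- a, the same probability if unsuppressed at baseline: 0.20-0.30

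The odds ratio is applied in both subgroups:

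- m = 0.80 becomes 7.6/8.6 = 0.884
- m = 0.90 becomes 17.1/18.1 = 0.945
- a = 0.20 becomes 0.475/1.475 = 0.322
- a = 0.30 becomes 0.814/1.814 = 0.449

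**Formulas.** With m1 and a1 the intervention values:

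- Baseline counted: difference = s(m1 − m)
- Months 6 and 12 only: difference = s(m1 − m) + (1 − s)(a1 − a)

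**Central case (s = 0.65, m = 0.80, a = 0.30).**

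- Baseline counted: 0.65 × 0.80 = 52.0% against 0.65 × 0.884 = 57.4%, a difference of 5.4 points.
- Months 6 and 12 only: 52.0 + 0.35 × 30 = 62.5% against 57.4 + 0.35 × 44.9 = 73.2% (from unrounded values), a difference of 10.7 points.

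**Ends of the range.**

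- Baseline counted, smallest (s = 0.50, m = 0.90): 2.2 points. Largest (s = 0.80, m = 0.80): 6.7 points.
- Months 6 and 12 only, smallest (s = 0.80, m = 0.90, a = 0.20): 3.6 + 2.4 = 6.0 points. Largest (s = 0.50, m = 0.80, a = 0.30): 4.2 + 7.4 = 11.6 points.

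**Power.** Simulated trials with logistic regression, 150 per arm, two-sided 0.017. The central-case ranges show the spread between repeated runs.

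| Endpoint and model | Central case | Across scenarios |
|---|---|---|
| Baseline counted, group only | 6-8% | about 2-13% |
| Months 6 and 12, group only | 30-34% | about 13-39% |
| Months 6 and 12, group plus baseline suppression | 42-44% | about 20-50% |

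**Sensitivity to the assumptions.** With poorer maintenance (m 0.60-0.80) and s 0.50-0.90, the normal approximation gives 4.2-12.6 points and 5-44% power with baseline counted. With months 6 and 12 only it gives 8.8-14.5 points and 26-56%. If only those unsuppressed at baseline benefit (a from 0.20 to 0.50, m equal in both arms), the difference is exactly 0 with baseline counted. Without it, the difference is (1 − s) × 30 points: 15 points at s = 0.50 and 3 points at s = 0.90.

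**The case against.** A reader might infer that the plan defines success as suppression at baseline, 6 and 12 months. It does not. Those three points are the specimen schedule. A reading that uses only months 6 and 12 fits the text equally well, and the parallel HIV-negative endpoint counts tests within 12 months. Section 10.2 also defers to an outside guideline. That does not settle the matter here: the cited number, 218, is a paper on power for covariance structure models in the reference list, and the guideline report is number 216.

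A reader might also infer that the trial could not register any improvement. That is too strong. Even with baseline counted, better maintenance shows up in the primary endpoint. Section 10.3.1 also plans to compare other care-continuum outcomes, which could include gained suppression. However, the outcome it names for this stratum is retention, measured by the number of viral load tests. The Aim 3 models of change in suppression are directed at the two intervention networks, not at the control comparison.

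A maintenance endpoint may be deliberate, since section 1.1 speaks of sustained suppression. If so, preferring gain plus maintenance is partly a choice of estimand, and the plan should state that choice.

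The unadjusted model is not an error. Baseline failures are expected equally across randomised arms, so they cost power and do not bias the comparison. Adjustment is a gain in efficiency, and it changes the odds ratio from marginal to conditional.

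Finally, the size rests on assumed rates, and the recommended analysis still reaches only 20-50% power under them. Much of the shortfall lies in the sample size calculation. These points limit the claim. They do not remove the need to say which specimens count.

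**Conclusion.** The concern holds conditionally. Sections 10.2 and 10.3.1 leave open whether the baseline specimen counts. If it does, the HIV-positive primary endpoint measures maintenance only and gives no credit for newly gained suppression. Under the assumed rates, that reduces the detectable arm difference from about 6-12 points to about 2-7 points, and power from about 13-39% to about 2-13%. Adjusting for baseline suppression raises power to about 20-50% under the months 6 and 12 reading, so it is worth having even if the sponsor never meant baseline to count.

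The direction follows from the definition. The size depends on rates that the documents do not give, and on the odds ratio of 1.9 applying in both subgroups. The documents do not support saying that baseline is part of the endpoint by definition, that improvement cannot be detected at all, or that the comparison is biased.

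**What to change.** - In 10.2 and 10.3.1, define HIV-positive success as suppression at both the 6- and 12-month specimens. Keep suppression at every specimen, baseline included, as a secondary endpoint. If maintenance alone is the intended target, say so and align the wording of Aim 1.
- In the HIV-positive primary model, replace group alone with group plus baseline suppression (yes, no, or specimen missing). The missing category keeps participants without a usable baseline specimen in the analysis.
- Report the effect separately for those suppressed and those unsuppressed at baseline.
- Because the adjusted odds ratio is conditional, also report the marginal risk difference.
- Record the collection date of each baseline specimen, and run a sensitivity analysis that treats specimens collected after randomisation as missing. Shipping the kit earlier would not by itself secure a pre-randomisation specimen, given the 45-day return window.

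The cost is revised wording in two sections, one recorded date and one sensitivity analysis, with no extra participants, visits or tests. The change should be made before outcome data are examined by arm.
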